- Open-label Treatment: Up to 36 weeks treatment with ferric maltol.
- End of Study: Week 52 or premature discontinuation.
- Post-treatment safety follow-up: 14 days following discontinuation of study medication.

Subjects that develop a ≥ 0.5 g/dL decrease from baseline in Hb that falls below 8.0g/dL on 2 consecutive weeks will be discontinued from study treatment.

Subjects who discontinue from study treatment prior to Week 16 will be encouraged to continue with study visits and assessments up to and including assessments at week 16.

Number of Subjects

Approximately 168 subjects.

Inclusion Criteria

All of the following criteria must be met to randomize a subject in the study:

1. Ability to understand the information given in the Independent Ethics Committee (IEC) or Institutional Review Board (IRB) approved information sheet and consent form. Must sign and date the informed consent and authorization to use protected health information (PHI) in accordance with national and local subject privacy regulations prior to any study mandated procedure.
2. Willing and able to comply with study requirements.
3. Age ≥ 18 years at the time of informed consent.
4. A current diagnosis of CKD with an estimated glomerular filtration rate (eGFR) of <60 mL/min/1.73m² and ≥ 15 mL/min/1.73m², as calculated using the abbreviated version of the Modified Diet in Renal Disease equation (MDRD) assessed via screening laboratory results.
5. Iron deficiency anemia defined by the following criteria assessed via screening laboratory results:
 - a. Hb <11.0 g/dL and ≥ 8.0 g/dL
 - b. AND ferritin <250 ng/mL with a Transferrin saturation (TSAT) $<25\%$
OR ferritin <500 ng/mL with a TSAT of $<15\%$
6. Female subjects of childbearing potential (including perimenopausal females who have had a menstrual period within 1 year prior to screening) must agree to use a reliable method of contraception until study completion

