- Any dose or frequency changes to myelosuppressants during the double-blind treatment period.
- Requirement for major surgery. Minor surgeries not associated with significant blood loss, in the Investigator's judgement, are permitted (e.g. surgery related to fistulae or vascular access, minor dental extractions, incision and drainage of abscess or simple excisions).

Subjects who discontinue study treatment prior to Week 16 will be encouraged to continue with study visits and assessments up to and including assessments at week 16.

**Investigational
Medicinal
Product**

Ferric maltol, 30 mg capsules or matching placebo twice daily. To be taken orally first thing in the morning before breakfast and last thing at night before bed. Capsules must be taken on an empty stomach with water only.

**Statistical
Methods**

Sample size calculation

A sample size of 135 subjects (Randomized 2:1, ferric maltol:Placebo, 90 in the ferric maltol group and 45 placebo) will have 95% power to detect a statistically significant treatment difference of 1.0g/dL between ferric maltol and placebo on the primary endpoint, using a two-sided 0.05 significance level. This calculation assumes a common standard deviation of 1.5g/dl which is based on a pooled estimate of SDs obtained from published trials. Assuming a drop-out rate of 20%, approximately 168 subjects total will be recruited. Subjects will be stratified based on baseline Hb value and eGFR.

Statistical Methods

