4.5.1 Study Population

Adult subjects will be enrolled who have a diagnosis of CKD with an eGFR of < 60 and at least $15 \text{ mL/min/1.73m}^2$. It is anticipated that this population will in general have less significant renal disease and comorbidities and be better able to tolerate the placebo phase of the study. Subjects will also have IDA as defined by Hb, ferritin and TSAT levels. Subjects should not be severely anemic and so will have $\text{Hb} \geq 8.0 \text{ g/dL}$. Subjects who have recently received IV iron, a blood transfusion or renal transplant will not be permitted to enter the study.

All subjects entering this study will be anemic ($\text{Hb} < 11.0 \text{ g/dL}$) which falls below the lower limit of normal Hb (13.5 g/dL for males, 12.0 g/dL for females per KDOQI 2006) for investigational purposes since the benefits to subjects being treated with ferric maltol with a Hb between 11 g/dL and the lower limit of normal could be marginal. Additionally, the cut-off of 11.0 g/dL is in line with KDOQI 2006 who specify a target Hb level of 11 g/dL or greater.

The inclusion criteria of $< 250 \text{ ng/mL}$ ferritin with a $< 25\%$ TSAT and or a $< 500 \text{ ng/mL}$ ferritin with a $< 15\%$ TSAT is indicative of iron deficiency and representative of the population likely to benefit from iron treatment.

Subjects who develop Hb concentration decreases of $\geq 0.5 \text{ g/dL}$ from baseline that falls below 8.0 g/dL

on 2 consecutive weeks will be withdrawn from the study and corrective measures implemented outside of the study. Withdrawal from the study would also be possible based on any AE, including anemia related symptoms, which the Investigator deemed significant. There is little data available on long or medium term Hb changes in CKD placebo treated subjects, so it is not possible to accurately predict how many subjects may have to withdraw during the 16 week placebo controlled period. However a study looking at ESA treatment in over 2000 anemic, CKD diabetic patients followed for 2.3 years showed that 55% of patients on placebo and without ESA treatment maintained a Hb >9.0 g/dL and that on average, Hb levels were either stable or increased in both the active and placebo groups (Skali 2013). The Hb decline in this study is not reported separately for hemodialysis and non-dialysis subjects, nor by iron replete or deficient subjects, however over a 2 year period the Hb decline did appear slow for most patients.

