4.6 RISK-BENEFIT EVALUATION

KIDGO recommends initiating treatment for IDA with oral ferrous products which are associated with GI side effects. If unsuccessful IV iron administration should be considered (see section 5.2).

This is in accordance with the labelled warnings of marketed oral iron products. The Summary of Product Characteristics (SPCs) for the various OFPs which warn that oral iron salts may have a corrosive effect that may exacerbate the symptoms associated with certain GI disease states such as peptic ulcer disease or IBD (e.g., UC). But despite this warning there are limited comparative data from prospective clinical trials investigating the AE profile of marketed oral iron products as compared to placebo or active comparators or comparing IBD to different patient populations.

The dose chosen for the Phase 3 development program, 30 mg bid, has been shown to be effective and well-tolerated in IDA patients with IBD for up to 64 weeks of treatment. In contrast to other marketed iron products, in particular ferrous drugs, the sugar derivative maltol strongly chelates iron, stabilizes iron in the less toxic ferric (Fe³⁺) form and renders it readily available for absorption in the intestinal tract. Consequently, the frequency of typical adverse effects is hypothesized to be reduced with administration of ferric maltol. This hypothesis is confirmed by ferric maltol being well-tolerated in patients who are intolerant to oral ferrous products in clinical studies ST10-01-301 and ST10-01-302; furthermore, unlike oral ferrous products, ferric maltol did not increase flare of underlying disease in these patients compared to placebo treatment.

The current study design does not pose additional risk for the subjects as no additional interventional procedures are planned during the study period, except for blood sampling similar to clinical routine. The patients randomized to placebo will be monitored and withdrawn should the

Hb fall ≥ 0.5 g/dL from baseline that falls below 8.0g/dL on 2 consecutive weeks.

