6.5 INDIVIDUAL WITHDRAWAL CRITERIA

Subjects have the right to withdraw consent without prejudice at any time during the study. If a subject withdraws consent, the Investigator should make a reasonable effort to determine the cause. All withdrawn subjects should have an End of Study Visit and a follow-up call 14 days after the last dose of study drug (if the subject agrees in the case of withdrawn consent).

Subjects who discontinue study treatment prior to Week 16 will be encouraged to continue with study visits and assessments up to and including assessments at week 16.

Subjects may be discontinued prematurely during the study for the following reasons:

- Withdrawal of informed consent.
- Unwillingness or inability to comply with protocol requirements.
- Pregnancy or not using a reliable method of birth control if female of childbearing potential.
- A ≥ 0.5 g/dL decrease from baseline in Hb that falls below 8.0g/dL on 2 consecutive weeks.
- Ferritin >700 ng/mL with a TSAT of $>50\%$ sustained for 2 consecutive weeks.
- SAEs that are judged by the Investigator to be related to study drug.
- Use of prohibited concomitant medications.
- Initiation of dialysis.
- Blood transfusions or donations for any cause.
- Any dose or frequency changes to myelosuppressants and/or ESAs (greater than 20% over an 8 week period) during the double-blind treatment period.
- Requirement for major surgery. Minor surgeries not associated with significant blood loss, in the Investigator's judgement, are permitted (e.g. surgery related to fistulae or vascular access, minor dental extractions, incision and drainage of abscess or simple excisions).

The reason for study drug discontinuation and the date of last dose should be recorded in the CRF.

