8.4 EMERGENCY UNBLINDING

Under normal circumstances, the blind should not be broken. The blind should be broken only if specific emergency treatment would be dictated by knowing the treatment status of the subject. It is highly unlikely that this situation will occur during this study. In such cases the Investigator can break the blind via the IXRS/randomization system. The system will encourage the Investigator to discuss the situation with Sponsor prior to breaking the code. Un-blinding will result in discontinuation of the subject from the study treatment and withdrawal from the study.

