9 STUDY PROCEDURES

9.1 DESIGN SCHEMATIC

9.2 SCHEDULE OF ASSESSMENTS

PERIODS	SCREENING	RANDOMIZED TREATMENT					OPEN-LABEL TREATMENT					FOLLOW-UP
Visit Duration	1-14 days	16 weeks					36 weeks					14 days after last dose ³
Visit Number	1	2	3	4	5	6	7	8	9	10	11	12
Visit Name	Screening Period ¹	Randomization	Week 4	Week 8	Week 12 (Telephone)	Week 16 End of Randomized Treatment Period	Week 20 (Telephone)	Week 24	Week 32	Week 42	Week 52 End of Study ²	Telephone Follow-up
Visit Window		14 days from Screening ¹	±3 days of Randomization			±7 days of Randomization					14-21 days after last dose of study drug	
Informed Consent	X											
Demographics	X											
Medical History	X											
Concomitant Medications and Procedures	X	X ⁴	X	X	X	X	X	X	X	X	X	X
Physical Examination		X				X					X	
Vital Signs		X ⁴				X					X	
12-Lead ECG		X ⁴									X	
Urine Pregnancy Test	X	X ⁴	X	X		X		X	X	X	X	
Hematology, Chemistry and Iron markers	X	X ⁴	X	X		X		X	X	X	X	
Population PK Sampling ⁵		X ⁴	X			X					X ⁵	
eGFR	X					X					X ⁵	
Retention Samples ⁵		X ⁴				X					X	
Eligibility Confirmation and Randomization		X ⁴										
Dispense Study Drug		X	X	X		X		X	X	X		
Return Study Drug			X	X		X		X	X	X	X	
Adverse Events		X	X	X	X	X	X	X	X	X	X	X

Note: unscheduled visits may be required (e.g. repeat laboratory sampling or safety assessments).

1. *A subject may be retested once for laboratory criteria that do not meet protocol criteria so long as randomization occurs no more than 14 days from the initial test result (if eligible).*

Subjects who withdraw from the study before Week 16 should have assessments conducted per Week 16/ End of Randomized Treatment Period or per Week 52/End of Study if withdrawn after Week 16. Subjects who discontinue from study treatment prior to Week 16 will be encouraged to continue with study visits and assessments up to and including assessments at week 16.

2. *Follow-up call not required if the subject prematurely discontinued treatment and the End of Study Visit occurred 14 days after the last dose taken.*
3. *Laboratory sampling and assessments must be completed prior to the first dose of study treatment.*
4. *Population PK samples are only required at Week 52 / End of Study visit if the subject has discontinued treatment prior to Week 16. Retention samples only applicable for sites with access to a -70/80°C freezer for storage.*

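### The Hb-fall stopping rule ends treatment in the synopsis but ends study participation in section 4.5.1, and the status of the exit Hb is undefined: a low-severity wording conflict

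*Combined protocol and SAP*

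**What the plan says.** The trigger is the same wherever it appears: Hb down by at least 0.5 g/dL from baseline and below 8.0 g/dL on 2 consecutive weeks. The stated consequence differs.

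- **Synopsis, Design:** such subjects "on 2 consecutive weeks will be discontinued from study treatment". The next sentence, repeated in substance under Withdrawal Criteria, reads "Subjects who discontinue study treatment prior to Week 16 will be encouraged to continue with study visits and assessments", up to and including Week 16.
- **Section 4.5.1:** such subjects "on 2 consecutive weeks will be withdrawn from the study and corrective measures implemented outside of the study".
- **Section 4.6:** "The patients randomized to placebo will be monitored and withdrawn should the" Hb meet the trigger. It does not say withdrawn from what.
- **Section 6.5, Individual Withdrawal Criteria:** the trigger is one bullet under "Subjects may be discontinued prematurely during the study for the following reasons". The section also says "All withdrawn subjects should have an End of Study Visit and a follow-up call 14 days after the last dose of study drug", and it repeats the encouragement to attend to Week 16 after stopping treatment.

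Elsewhere the protocol treats the two statuses as distinct. Section 8.4 names both: "Un-blinding will result in discontinuation of the subject from the study treatment and withdrawal from the study". The footnotes to section 9.2 give each its own path. For study withdrawals, "Subjects who withdraw from the study before Week 16 should have assessments conducted per Week 16/ End of Randomized Treatment Period". Subjects who only stop treatment are encouraged to attend through Week 16.

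The primary endpoint is Hb change from baseline to Week 16 in all randomized subjects (5.3, 11.3.3). Missing Week 16 change is multiply imputed, guided by baseline, Week 4 and Week 8 Hb and gender (11.2.1).

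**The concern.** The rule selects subjects on a poor value of the variable that is the primary endpoint, and probably selects a larger share of placebo than of active subjects. Under 4.5.1 their follow-up ends at the trigger; under the synopsis their Week 16 Hb is measured if they attend. If sites follow different texts, the same clinical event produces different data at different sites.

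The second gap concerns the exit Hb. A subject withdrawn at, say, Week 5 has the Week 16 assessments done then. Section 11.2.1 does not say whether that Hb is the Week 16 value or whether the Week 16 value is missing and imputed. An SAP can settle the handling, but it cannot recover a Week 16 Hb that was never drawn.

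**Working it through.** **1. The plan's own figure.** Inputs from 11.1: difference 1.0 g/dL, SD 1.5, two-sided 0.05, 90 active and 45 placebo. The standard error is 1.5 × √(1/45 + 1/90) = 0.274. Power = Φ(1.0/0.274 − 1.96) = Φ(1.69) = 95.5%, so the stated 95% reproduces. Recruitment: 135/0.8 = 168.75, against approximately 168 stated.

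**2. Assumed inputs.** Section 4.5.1 says the number of withdrawals cannot be accurately predicted, so a simulation (400,000 subjects per arm) used assumed ranges:
- Baseline Hb: mean 9.5 to 10.0, SD 0.8, restricted to 8 to 11 g/dL.
- Week 16 change: SD 1.0 to 1.5; SD at Weeks 4 and 8 is 0.6 and 0.75 times that; correlation between visits 0.5 to 0.7.
- Mean change: 0 on placebo; on active 0.25, 0.5 and 1.0 at Weeks 4, 8 and 16.
- A low Hb at Week 4 or 8 is rechecked a week later in 50 to 100% of cases. No weekly Hb is scheduled, and Week 12 is a telephone visit.
- Under the synopsis rule, 50 to 100% of triggered subjects attend Week 16 and the rest are imputed within arm; corrective treatment adds 1 or 2 g/dL.

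Of 168 subjects randomized 2:1 (56 placebo, 112 active), about 1 to 8 placebo and 1 to 9 active subjects meet the rule.

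**3. Expected treatment difference by handling** (planned value 1.0; simulation error about 0.01):

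| Week 16 value for triggered subjects | Difference, g/dL |
|---|---|
| Imputed within arm from baseline, Week 4, Week 8 Hb | about 1.00 |
| Imputed from the same Hb values, no treatment term | about 0.92–1.00 |
| Exit Hb used as Week 16 | about 0.96–1.00 |
| Measured after a corrective rise of 1 g/dL | about 0.93–0.99 |
| Measured after a corrective rise of 2 g/dL | about 0.87–0.99 |

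**4. Where the differences come from.** The trigger is an observed low Hb at Week 4 or 8, and both values are in the imputation list. Within-arm imputation recovers the mean uncorrected Week 16 change of triggered placebo subjects to within about 0.02 g/dL. With no corrective rise, the measured and within-arm imputed analyses agree. The dilution in the last two rows is therefore the rescue effect: share attending × rise × (placebo proportion − active proportion triggered). In the most extreme case, 8.1/56 = 14.5% and 9.2/112 = 8.2%, a gap of 6.3 points. With full attendance and a rise of 2, the dilution is 2 × 0.063 = 0.13, which leaves about 0.87.

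**5. Effect on power** at 90/45, SD 1.5, from the formula in step 1: at 0.96, Φ(3.51 − 1.96) = 93.9%; at 0.92, Φ(3.36 − 1.96) = 91.9%; at 0.87, Φ(3.18 − 1.96) = 88.8%.

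**The case against.** The strongest reply is that 4.5.1 is population rationale and that the operational text leans the other way. Section 6.5 closes its list by asking for the reason for stopping study drug and the date of last dose, which points to treatment discontinuation. The encouragement to continue to Week 16 stands next to the list in both 6.5 and the synopsis. This largely stands: a careful reader would favour the synopsis rule. It does not remove the conflict. Section 6.5 carries a withdrawal heading, prescribes an End of Study Visit for withdrawn subjects, and never states the consequence for this trigger. The only explicit statement in the body of the protocol is the opposite one in 4.5.1.

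A second reply is that missing Week 16 values are imputed and that carry-forward appears only as a sensitivity analysis (11.2.3), so an exit Hb would presumably not be used. That is a reasonable inference, but 11.2.1 does not say it.

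A reader might infer more: that the lost Week 16 values seriously bias the primary result. The documents do not support this. They give no trigger rate, and the triggering Hb values feed the imputation. The larger shifts in the table come from the assumed corrective rise, not from missing data. Lost data matter mainly if the imputation omits treatment; 11.2.1 does not list treatment among its guiding variables, but neither does it exclude it.

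**Conclusion.** The conflict is real and lies in current text. For one trigger, the synopsis and 4.5.1 assign different statuses; 4.6 is unspecific; and 6.5 leans towards stopping study drug without saying so. A site following 4.5.1 would collect no Week 16 Hb in subjects selected on the primary outcome, and the role of their exit Hb is undefined.

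Severity is low. On the assumed rates, following 4.5.1 moves the expected difference from 1.0 to no lower than about 0.92 g/dL, and within-arm imputation leaves it at about 1.00. Power stays near 92% or above, so the conclusion at the planned effect does not change. These sizes depend on the assumed baseline distribution, correlations and retest rate; the protocol supplies only the SD of 1.5 and the planned effect. The case for acting is consistent follow-up across sites at almost no cost, not rescue of the primary result.

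**What to change.** 1. In 4.5.1 and 4.6, replace withdrawal with: *discontinued from study treatment and encouraged to continue visits and assessments to Week 16; corrective treatment may be given.*
2. In 6.5 and the synopsis withdrawal list, state that the Hb-fall bullet means stopping study treatment, not follow-up. Say the same for the prohibited-medication and transfusion bullets. Transfusion, IV iron and ESAs are not permitted under 6.4.1, so correcting the anemia with any of these would trigger those bullets and reopen the question.
3. In 11.2.1, add that an Hb taken at early withdrawal outside the Week 16 window is not the Week 16 value, which is treated as missing and imputed. The LOCF sensitivity analysis is unaffected.

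The cost is wording only; Week 16 attendance after stopping treatment is already planned in the synopsis, 6.5 and 9.2. Attendance is only encouraged, so some values will still be imputed.

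The downside is that some Week 16 values will follow corrective treatment. Used as measured, they may dilute the estimate to about 0.93–0.99 g/dL with a rise of 1, or 0.87–0.99 with a rise of 2, on the assumed rates. Collecting the value does not decide how it is used. That estimand choice, and the responder status of these subjects, stay with the SAP.

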4.5.2 Study Treatment Duration

Maximum treatment duration in this study is 52 weeks. Primary efficacy and safety of ferric maltol will be evaluated after the first 16 week double-blind phase after which time all ongoing subjects will receive open-label ferric maltol for up to an additional 36 weeks. Long-term safety and efficacy of ferric maltol will be examined during the open-label portion of the study. As there is a physiologically-determined limit on the amount of iron that can be absorbed from oral iron medication, the study has a 16 week placebo controlled period. This has been selected as the maximum duration likely to be clinically acceptable to achieve a meaningful Hb rise in IDA CKD patients.

This study treatment duration will continue until the last randomized subject completes the study at Week 52 or prematurely withdraws from the study.

4.6 RISK-BENEFIT EVALUATION

KIDGO recommends initiating treatment for IDA with oral ferrous products which are associated with GI side effects. If unsuccessful IV iron administration should be considered (see section 5.2).

This is in accordance with the labelled warnings of marketed oral iron products. The Summary of Product Characteristics (SPCs) for the various OFPs which warn that oral iron salts may have a corrosive effect that may exacerbate the symptoms associated with certain GI disease states such as peptic ulcer disease or IBD (e.g., UC). But despite this warning there are limited comparative data from prospective clinical trials investigating the AE profile of marketed oral iron products as compared to placebo or active comparators or comparing IBD to different patient populations.

The dose chosen for the Phase 3 development program, 30 mg bid, has been shown to be effective and well-tolerated in IDA patients with IBD for up to 64 weeks of treatment. In contrast to other marketed iron products, in particular ferrous drugs, the sugar derivative maltol strongly chelates iron, stabilizes iron in the less toxic ferric (Fe³⁺) form and renders it readily available for absorption in the intestinal tract. Consequently, the frequency of typical adverse effects is hypothesized to be reduced with administration of ferric maltol. This hypothesis is confirmed by ferric maltol being well-tolerated in patients who are intolerant to oral ferrous products in clinical studies ST10-01-301 and ST10-01-302; furthermore, unlike oral ferrous products, ferric maltol did not increase flare of underlying disease in these patients compared to placebo treatment.

The current study design does not pose additional risk for the subjects as no additional interventional procedures are planned during the study period, except for blood sampling similar to clinical routine. The patients randomized to placebo will be monitored and withdrawn should the

Hb fall ≥ 0.5 g/dL from baseline that falls below 8.0g/dL on 2 consecutive weeks.

The intervals of Hb measurement within the schedule of study visits fall within KDOQI guidelines on monitoring Hb in patients receiving iron replacement. All patients who complete the randomized phase and remain on-treatment will enter an extended open-label phase of ferric maltol treatment and potentially benefit from iron replacement. The safety profile of ferric maltol as established from completed studies is considered acceptable and therefore the overall benefit/risk to subjects entering this study is also acceptable.

Refer to the Investigator's Brochure for further details on risk/benefit assessment.

